3.1.2. Rationale for Dosing Regimen

A BIIB122 dose of 225 mg or placebo administered orally QD in a 1:1 randomization ratio is proposed for this study. Dose selection is based on the [REDACTED]

Clinical efficacy is hypothesized to require a dose level that [REDACTED]

[REDACTED] Confirmation of CNS LRRK2 pathway modulation is also desired since the primary Parkinson's disease pathology is in the CNS. The selected 225 mg QD dose is the lowest dose that satisfies the following requirements:

1. [REDACTED]

2. [REDACTED]

3. [REDACTED]

A [REDACTED] % reduction in pS935 LRRK2 was selected for the level of target engagement, since this magnitude of kinase inhibition is believed to be required to normalize the [REDACTED] in kinase activity demonstrated in LRRK2 *G2019S* variant carriers [Melachroinou 2020; Steger 2016; Wang 2021].

In Phase 1 healthy volunteers, there was a reduction in pS935 LRRK2 of \geq [REDACTED] % at doses \geq [REDACTED] mg daily and \geq [REDACTED] % reduction at doses \geq [REDACTED] mg QD daily. At doses \geq [REDACTED] mg QD, there was also a \geq [REDACTED] % reduction in pRab10 in PBMC, a direct substrate of LRRK2 kinase. In addition, a dose-dependent reduction in urinary [REDACTED] was observed at doses \geq [REDACTED] mg and median reduction in total LRRK2 protein in CSF was observed at doses \geq [REDACTED] mg QD. Similar biomarker results were demonstrated in the Phase 1b PD study where BIIB122 achieved pS935 LRRK2 kinase inhibition by \geq [REDACTED] % in whole blood and reduction of pRab10 in PBMC [REDACTED], as well as a reduction in urine [REDACTED] at the [REDACTED] mg dose.

Based on the currently available data, [REDACTED]

The placebo-controlled, double-blind treatment period in this study allows enough disease progression in the placebo group to detect an effect size of \geq 35% reduction in time to confirmed

CONFIDENTIAL

The information contained herein may not be used, disclosed, or published without the written consent of Biogen MA Inc.

worsening in MDS-UPDRS Parts II and III combined score with the current sample size. The minimum 96-week treatment period expands the safety exposure data for BIIB122.

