Sample Size Determination: A minimum of approximately [REDACTED] events would be required to detect a [REDACTED] relative treatment effect for BIIB122 [REDACTED] for the primary endpoint with [REDACTED] power, at the 2-sided significance level of [REDACTED]. Up to 2 potential interim efficacy analyses, pending regulatory feedback, may be conducted in which case approximately [REDACTED] events would be needed to achieve approximately [REDACTED] power for the study. With a sample size of approximately [REDACTED] participants per treatment group, followed for a minimum of [REDACTED] weeks ([REDACTED] weeks of treatment followed by [REDACTED] weeks of SFU) and a maximum of

CONFIDENTIAL

The information contained herein may not be used, disclosed, or published without the written consent of Biogen MA Inc.

█ weeks (█ weeks of treatment followed by █ weeks of SFU), a total number of up to █ events is expected to have been reached when all participants complete the planned treatment period and provides the study with approximately █ power with 2 potential IAs. These estimates assume a median time to confirmed worsening of █ weeks (approximately █ months) in the placebo group, and a █ annual exponential dropout/censoring rate.

Visit Schedule:

Study assessments conducted at each visit are listed in the Schedule of Activities ([Table 1](#)).

Duration of Study Participation:

The total study duration for each participant (including the Screening period) will be a minimum of approximately 103 weeks and a maximum of approximately 187 weeks as follows:

- 5-week Screening period █
- 96-week minimum to 180-week maximum (when the total number of events for the primary endpoint reaches approximately 200 events) double-blind, placebo-controlled treatment period
- █

Benefit-Risk Analysis:

There is a significant need for an effective disease modifying therapy that delays PD progression, which is not addressed by current therapies. Lysosomal dysfunction contributes to disease risk in PD patients, suggesting that therapeutics that reduce LRRK2 kinase activity may provide benefit for patients with PD.

The data from previous clinical studies with doses of up to 300 mg QD in participants with PD (28 days exposure), and up to 400 mg BID in healthy volunteers (14 days exposure)

CONFIDENTIAL

The information contained herein may not be used, disclosed, or published without the written consent of Biogen MA Inc.

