5. STUDY DESIGN

5.1. Study Overview

This Phase 3, multicenter, randomized, double-blind, placebo-controlled, parallel-group study is designed to evaluate the efficacy and safety of BIIB122 in approximately 400 participants with LRRK2-PD who are in the early stage of the disease. The study will be conducted at approximately 55 study sites globally. The study population is defined as participants with a clinical diagnosis of PD within 5 years of the Screening Visit, a mHY 1-2.5 (in OFF state), who carry a pathogenic variant in the LRRK2 gene (e.g., *G2019S*, *N1437H*, *R1441G*, *R1441C*, *R1441H*, *Y1699C*, or *I2020T*).

Randomization will be performed using IRT. Participants will be randomly assigned to receive BIIB122 225 mg or placebo orally QD in a 1:1 ratio. [REDACTED]

[REDACTED]

The double-blind placebo-controlled treatment period is a minimum of [REDACTED] weeks and could be as long as [REDACTED] weeks for each participant. The study duration depends on when the last enrolled participant has completed the [REDACTED] Visit and number of events for the primary endpoint reaches a minimum number to provide approximately [REDACTED] power for the study, which will be specified in the SAP, since the minimum number depends on the number, timing, and nature of planned interim analyses. Each participant will have a SFU Visit 2 weeks after the last dose. The majority of in-clinic visits occur at [REDACTED]-week intervals.

The safety of BIIB122 will be evaluated as follows:

Safety Cohort

[REDACTED]

[REDACTED]

CONFIDENTIAL

The information contained herein may not be used, disclosed, or published without the written consent of Biogen MA Inc.

[REDACTED]
[REDACTED]
[REDACTED]
(see [Figure 1](#)).

See [Appendix A](#) for details on procedures to follow in the event of a public health emergency.

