12.3. Methods of Analysis for Efficacy Endpoints

12.3.1. Analysis of the Primary Endpoints

The primary efficacy endpoint is time to confirmed worsening in MDS-UPDRS Parts II and III combined score over the treatment period. Confirmed worsening is defined as

[REDACTED]

[REDACTED]

[REDACTED]

[REDACTED]

CONFIDENTIAL

The information contained herein may not be used, disclosed, or published without the written consent of Biogen MA Inc.

[REDACTED]

[REDACTED]

[REDACTED]

[REDACTED]

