12.9. Interim Analyses

Up to 2 IAs, one earlier and one later in the study, pending regulatory feedback, may be performed for efficacy over the course of the study. A Lan-Demets alpha-spending function will be used to approximate the O'Brien Fleming for the interim and final analysis, to control the overall type I error alpha level at 0.05 two-sided. Additional details will be described in the SAP.

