12.10. Sample Size Considerations

A minimum of approximately [] events would be required to detect a \geq []% relative treatment effect for BIIB122 (hazard ratio = []) for the primary endpoint with \geq []% power, at the

CONFIDENTIAL

The information contained herein may not be used, disclosed, or published without the written consent of
Biogen MA Inc.

2-sided significance level of █%. Up to █ potential interim efficacy analyses, described in Section 12.9, may be conducted in which case approximately █ events would be needed to achieve approximately \geq █% power for the study. With a sample size of approximately █ participants per treatment group, followed for a minimum of █ weeks (█ weeks of treatment followed by █ weeks of SFU) and a maximum of █ weeks (█ weeks of treatment followed by █ weeks of SFU), a total number of up to █ events is expected to have been reached when all participants complete the planned treatment period and provides the study with approximately \geq █% power with █ potential IAs. These estimates assume a median time to confirmed worsening of █ weeks (approximately █ months) in the placebo group, and a █% annual exponential dropout/censoring rate. Placebo group progression rate assumptions are from █, and the assumed treatment effect size is based on survey results of physicians.

CONFIDENTIAL

The information contained herein may not be used, disclosed, or published without the written consent of
Biogen MA Inc.

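### Does the detectable effect worded as a 35% reduction in time to worsening show that the trial is sized for the wrong effect?

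*Combined protocol and SAP*

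**What the plan says.** The last paragraph of Section 3.1.2 (Rationale for Dosing Regimen) says that placebo progression over the treatment period is enough to detect an effect of at least "35% reduction in time to confirmed" and, after the page break, "worsening in MDS-UPDRS Parts II and III combined score with the current sample size".

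The other places that bear on the effect size are:

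- Section 12.3.1 defines the outcome: "The primary efficacy endpoint is time to confirmed worsening in MDS-UPDRS Parts II and III combined score over the treatment period".
- Section 12.10 gives the effect for sizing on the hazard scale, as a "relative treatment effect for BIIB122 (hazard ratio". The percentage, the hazard ratio and the power are blacked out.
- The Synopsis (Duration of Study Participation) ties the maximum treatment period to the point "when the total number of events for the primary endpoint reaches approximately 200 events".
- Section 5.1 leaves the required minimum number of events to the SAP and gives the allocation: "Participants will be randomly assigned to receive BIIB122 225 mg or placebo orally QD in a 1:1 ratio".
- Section 12.9 plans "Up to 2 IAs, one earlier and one later in the study", with O'Brien-Fleming-type spending "to control the overall type I error alpha level at 0.05 two-sided".

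**The concern.** The endpoint is a time to a bad outcome, so benefit means a longer time. Taken literally, a 35% shorter time on BIIB122 is harm: under exponential event times the hazard ratio would be 1/0.65 = 1.54.

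A reader who sees the slip can repair it in two ways. Correcting only the direction gives a 35% longer time. Correcting the quantity gives a 35% lower hazard. These are different effects: the second corresponds to a time about 54% longer (1/0.65 = 1.54). If the first were the design effect, about 200 events would be far too few.

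The sentence also carries the only visible figure for the effect, and Section 12.10 says the assumed effect came from a survey of physicians. It is natural to ask whether a delay given by clinicians was later used as a hazard reduction.

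**Working it through.** **Inputs.** Events d = 200 (Synopsis); 1:1 allocation (Section 5.1); two-sided alpha 0.05 and up to two looks (Section 12.9). The hazard ratio and target power are blacked out, so the 200 events cannot be strictly reproduced. The check is which reading of the 35% fits them.

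**Power (Schoenfeld, 1:1).** Power = Φ(|ln HR| × √d / 2 − 1.96), with √200 / 2 = 7.071.

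- 35% lower hazard, HR 0.65: 0.4308 × 7.071 − 1.96 = 1.086, so power is 86.1%.
- 35% longer time, HR 1/1.35 = 0.741: 0.3001 × 7.071 − 1.96 = 0.162, so power is 56.4%.

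Freedman's formula, Φ(√d × (1 − HR)/(1 + HR) − 1.96), gives 85.1% and 55.8%.

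**Interim looks.** The timing is not stated. With Lan-DeMets O'Brien-Fleming-type boundaries at assumed information fractions of 0.33/0.67, 0.40/0.70, 0.50/0.75 and 0.60/0.80, power at 200 events is 85.3% to 85.7% for HR 0.65 and 55.3% to 55.8% for HR 0.741. The assumed timing hardly matters.

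**Events required.** Schoenfeld: d = 4(1.96 + z_power)² / (ln HR)². Freedman: d = (1.96 + z_power)² × (1 + HR)² / (1 − HR)².

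| Reading | Power | Schoenfeld | Freedman |
|---|---|---|---|
| HR 0.65 | 80% | 170 | 175 |
| HR 0.65 | 85% | 194 | 200 |
| HR 0.65 | 90% | 227 | 234 |
| HR 0.741 | 80% | 349 | 354 |
| HR 0.741 | 85% | 399 | 405 |

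About 200 events is what a 35% hazard reduction needs at about 85% power. A 35% delay at that power would need about as many events as the roughly 400 participants to be randomized, which is not a design anyone would have written down with a 200-event target.

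**Can the 35% be a time ratio at all?** Under exponential times the ratio of placebo median to BIIB122 median equals the hazard ratio. At HR 0.65 the placebo time is therefore 35% shorter than the BIIB122 time. The number is coherent; the direction of the comparison, or the word time in place of hazard, is what went wrong.

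**The case for a change.** The strongest case for acting is that a Phase 3 protocol should not state its detectable effect in the harmful direction, and that the simplest repair leads to an effect for which power is about 56%. The slip is in current, fully visible text, and correcting it would cost one sentence. All of that is true.

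What does not stand is the step from a wrong word to a weak design. The 56% belongs to a claim of a 35% longer time, which the protocol does not make. Section 12.10, which governs sizing, uses a hazard ratio. Readers of the unredacted protocol see its value, and blacking it out in the public copy is not a fault of the plan. Section 12.1 lets the SAP override the protocol on statistical methods, and Section 5.1 leaves the minimum event count to the SAP. Nothing downstream takes its input from Section 3.1.2.

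The survey point is a guess. Section 12.10 does not say on which scale the physicians were asked, and nothing visible suggests that delay and hazard were confused.

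**Conclusion.** The wording in Section 3.1.2 is wrong in direction and does not match the hazard scale of Section 12.10. It is a clerical slip. The visible design figures agree with a 35% reduction in the hazard of confirmed worsening: about 86% power with 200 events, and 85.3% to 85.7% with two looks. No stated event count, sample size, power or boundary is shown to be wrong, and a statistician working from Section 12.10 and the SAP would not be misled.

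This rests on three assumptions: that the blacked-out hazard ratio is 0.65, that the final event count is about 200, and, for the conversions between hazard and time only, that event times are exponential. The documents use an exponential form explicitly only for dropout. Replacing time with hazard would be a harmless editorial tidy whenever the text is next revised, but it would alter no analysis, event target or conclusion, so the plan can stand as it is.

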3.2. Background

3.2.1. Overview of Parkinson's Disease

Refer to Section 3.1 in the Investigator's Brochure for detailed information.

3.2.2. Current Therapies for Parkinson's Disease

Currently approved treatments improve motor symptoms but do not address the underlying cause of PD. Over time, these symptomatic therapies lose effectiveness and are associated with increasing frequency and severity of adverse effects, such as dyskinesias and hallucinations. In addition, nonmotor symptoms, including depression, anxiety, sleep disorders, cognitive impairment, and dementia, are disabling and common features of PD but are poorly addressed by current therapies [Aarsland 1996; Khoo 2013; Lyons and Pahwa 2011; Seppi 2019; Truong 2008].

As such, PD patients inevitably experience mounting disabilities over the years to decades that they live with the disease [Hely 2005]. Thus, there is a significant need for an effective disease-modifying therapy to prevent the progressive motor and nonmotor disabilities.

3.2.3. Profile of Previous Experience With BIIB122

The safety, tolerability, and PK of orally administered BIIB122 has been evaluated in multiple Phase 1 clinical studies. See the Investigator's Brochure for detailed information on relevant nonclinical and clinical studies, both completed and ongoing.

As of 12 November 2022, a total of 340 participants have received at least 1 dose of BIIB122 (26 participants with Parkinson's disease and 314 healthy volunteers).

Variability following repeated dosing of BIIB122 was low-to-moderate across all doses from [REDACTED] mg to [REDACTED] mg QD (\leq [REDACTED]%) and [REDACTED] to [REDACTED] mg BID (\leq 35%). The mean CSF-to-unbound plasma concentration ratio ranged from approximately [REDACTED] to [REDACTED] across a dose range from [REDACTED] to [REDACTED] mg QD and from [REDACTED] to [REDACTED] for doses of [REDACTED] to [REDACTED] mg BID in healthy participants. This ratio was approximately [REDACTED] for doses from [REDACTED] to [REDACTED] mg QD in participants with Parkinson's disease. Taken together, these data suggest [REDACTED].

Following single or multiple oral doses from 15 to 300 mg QD, BIIB122 was rapidly absorbed, with T_{max} ranging from 1.0 to 1.5 hours postdose. The $t_{1/2}$ of BIIB122 varied from approximately 47 (\pm 11) hours at 45 mg to 93 (\pm 102) hours at 300 mg, after 10 daily doses. Following 10 oral daily doses from 45 mg to 300 mg, BIIB122 showed accumulation in C_{max} [REDACTED] and AUC [REDACTED]. After multiple oral daily administration of BIIB122 [REDACTED] mg, plasma C_{max} and AUC were [REDACTED] on Day 10 (healthy participants) and Day 28 (PD patients), suggesting that steady state is reached by Day 10.

CONFIDENTIAL

The information contained herein may not be used, disclosed, or published without the written consent of Biogen MA Inc.

Data from 2 DDI studies (Studies DNLI-C-0002 and DNLI-C-0005) established BIIB122 as [REDACTED] to coadministration with [REDACTED], with approximately [REDACTED]-fold increase in AUC, approximately [REDACTED] increase in C_{max} , and [REDACTED] from [REDACTED]-fold to [REDACTED]-fold when coadministered with either diltiazem XL (moderate 3A4 inhibitor) or itraconazole (strong 3A4 inhibitor) at steady-state. In Study DNLI-C-0008, the impact of BIIB122 on the PK of a single oral dose of MDZ, a model victim CYP3A substrate, was assessed. The study results characterized BIIB122 as a [REDACTED], as demonstrated by the observed [REDACTED] % [REDACTED] in MDZ AUC_{inf} , which falls within the FDA definition of [REDACTED] of greater than [REDACTED] % and less than [REDACTED] % [FDA 2020].

Based on safety data from Parts 1 through 3 of the Phase 1b study (DNLI-C-0003), BIIB122 was generally well tolerated at 80-, 130-, or 300-mg QD for 28 days in participants with Parkinson's disease. No deaths, other SAEs, or AESIs were reported. Two participants had a TEAE leading to study drug discontinuation: 1 participant in the BIIB122 130-mg QD group (hypotension) and 1 participant in the BIIB122 300-mg QD group (hypotension). The TEAEs reported for ≥ 2 participants that were more frequent for BIIB122 than placebo across all doses tested were headache, back pain, nasopharyngitis, procedural pain, nausea, dizziness, hypotension, orthostatic hypotension, and fatigue. The majority of TEAEs were mild. Two participants (5.6%) experienced a severe TEAE (asymptomatic hypotension [80 mg/130 mg/placebo cohort] and headache [300-mg/placebo cohort]).

No other clinically significant changes in safety laboratory tests, vital signs, ECG, PFTs, C-SSRS, or neurological examination results were observed.

Administration of BIIB122 80-, 130-, and 300-mg doses QD for 28 days in participants with Parkinson's disease resulted in [REDACTED] inhibition of LRRK2 activity, as measured by median percent reductions from baseline in whole-blood pS935 LRRK2 and PBMC pT73 Rab10 levels [REDACTED].

3.3. Benefit-Risk Assessment

While the safety and efficacy of BIIB122 will be confirmed in this study, it is hypothesized that reducing LRRK2 kinase activity may provide benefit for patients with PD independent of LRRK2 genetic status. The proposed population for this study will consist of participants with early-stage PD with pathogenic LRRK2 variants. Currently approved treatments improve motor symptoms but do not address the underlying cause of the disease. Thus, there is a significant need for an effective disease-modifying therapy that delays progression, which is not addressed by current therapies. The pharmacodynamic response profile of BIIB122 [REDACTED] mg QD is supportive of a potential efficacy as detailed in Section 3.1.2.

Nonclinical safety pharmacology studies were performed to determine the effects of BIIB122 on the cardiovascular, respiratory, and neurological systems. [REDACTED]

[REDACTED] was observed in rats and monkeys only at [REDACTED] QD. Similarly, [REDACTED] were observed in monkeys at [REDACTED] QD and included [REDACTED] [REDACTED] were observed in a [REDACTED]

CONFIDENTIAL

The information contained herein may not be used, disclosed, or published without the written consent of Biogen MA Inc.

[REDACTED]-finding study. These findings were reversed following a [REDACTED]-hour treatment-free period. [REDACTED]. The nonclinical toxicology studies for the duration of up to [REDACTED]-weeks in rats and [REDACTED]-weeks in monkeys indicated that the [REDACTED] are [REDACTED]. The NOAEls were [REDACTED] mg/kg (rat) and [REDACTED] mg/kg (monkey), with corresponding AUCs as presented in Table 2. Histological evaluations showed the multifocal vacuolation of Type II pneumocytes in monkeys. This finding was fully reversible and considered nonadverse. It has been reported that multiple and structurally distinct LRRK2 inhibitors cause pharmacologically driven lung findings consisting of lamellar body changes in type II pneumocytes [Baptista 2020; Fuji 2015]. Renal findings in monkeys were limited to a nonadverse and partially reversible minimal to slight tubular cell pigment. Renal findings were morphologically consistent with the early manifestations of findings reported in LRRK2 knockout mice related to pharmacological inhibition of the LRRK2 [Baptista 2013; Herzig 2011; Ness 2013]. Detailed information can be found in the Investigator's Brochure. Overall, the results of the nonclinical safety studies in rats and monkeys support continued development of BIIB122 and the inclusion of women of childbearing potential and men.

Table 2: Safety Margins

Study	Dose	Total AUC μM*h	AUC Safety Margin to NOAEL in Rats	AUC Safety Margin to NOAEL in Monkeys
Chronic toxicology in rats ([REDACTED]-week)	[REDACTED] mg/kg ¹	[REDACTED]	NA	NA
Chronic toxicology in monkeys ([REDACTED]-week)	[REDACTED] mg/kg ¹	[REDACTED]	NA	NA
Phase 1 ² ([REDACTED] and [REDACTED] days)	[REDACTED] mg QD	[REDACTED]	[REDACTED]	[REDACTED]
	[REDACTED] mg QD	[REDACTED]	[REDACTED]	[REDACTED]
	[REDACTED] mg QD	[REDACTED]	[REDACTED]	[REDACTED]
Phase 1 ([REDACTED] days)	[REDACTED] mg BID	[REDACTED]	[REDACTED]	[REDACTED]
	[REDACTED] mg BID	[REDACTED]	[REDACTED]	[REDACTED]
Phase 1 (DNLI-C-0008) ([REDACTED] days)	[REDACTED] mg QD	[REDACTED]	[REDACTED]	[REDACTED]

¹ NOAEL

² Results from [REDACTED]-day study DNLI-C-0001 are shown. The AUC in [REDACTED]-day study at [REDACTED] mg QD was [REDACTED] μM*hr

Results from previous clinical studies with doses of up to 300 mg QD in participants with PD (28 days exposure), and up to 400 mg BID in healthy volunteers (14 days exposure) demonstrate that BIIB122 is generally safe and well tolerated. Detailed safety information can be found in the Investigator's Brochure.

CONFIDENTIAL

The information contained herein may not be used, disclosed, or published without the written consent of Biogen MA Inc.

The dose selected for Study 283PD302 is 225 mg QD, which corresponds to safety margins of [REDACTED] - and [REDACTED] -fold for AUC at the NOAEL in monkeys and rats, respectively, based on the largest AUC exposure reported in study DNLI-C-0008 ([Table 2](#)).

In addition, higher drug plasma exposures were achieved in previous clinical trials of BIIB122 in healthy volunteers and PD participants. The AUC at the dose of [REDACTED] mg BID was [REDACTED] $\mu\text{M}^*\text{h}$ after 14 days of BIIB122 administration ([Table 2](#)).

This study will include a Safety Cohort, and safety measures will include specific eligibility criteria to reduce risk to participants, monitoring of safety laboratory values at baseline and during study, real-time monitoring of SAEs, real-time monitoring of protocol-defined AESIs, safety monitoring by an IDMC, and predefined dose stopping criteria with regard to [REDACTED], [REDACTED]. Further details on the Safety Cohort and the Safety Monitoring Plan can be found in Section [5.1](#) and [Appendix B](#), respectively.

[REDACTED]

[Whiffin 2019].

In conclusion, the risks identified from nonclinical and clinical safety studies are manageable. Given the unmet need for a therapeutic treatment that may slow the progression of PD, BIIB122 has an overall favorable benefit-risk profile supporting further continued development of BIIB122 in PD patients.

CONFIDENTIAL

[figure not shown]
The information contained herein may not be used, disclosed, or published without the written consent of Biogen MA Inc.

